7.1.2.6.3 Solid Tumors and B Cell Lymphoma

7.1.2.6.3.1 Imaging

The process for image collection and transmission to the central vendor can be found in the Site Imaging Manual. Initial imaging (CT Scans, MRI, CT/PET, etc.) must be performed within 28 days prior to the first dose of treatment, and should be repeated at week 12 (or Day 84), at week 24 and every 12 weeks until confirmed disease progression, the start of new anti-cancer therapy, withdrawal of consent, death or end of the study, whichever comes first.

Table 9 below outlines the imaging that should be performed for each tumor type. The same imaging technique should be performed at each time point.

Table 9 Imaging by Anatomical Coverage

Organ coverage /Indication	B-Cell lymphoma	SCCHN	Melanoma	Breast Cancer With dermal metastasis
Chest, Abdomen	Mandatory	Mandatory	Mandatory	Mandatory
Pelvis	Mandatory	If clinically indicated	Mandatory	Mandatory
Soft Tissue Neck	If clinically indicated	Mandatory	If clinically indicated	If clinically indicated
Head	If clinically indicated	If clinically indicated	If clinically indicated	If clinically indicated
Skin Photography	NA	NA	If clinically indicated for cutaneous skin lesions	If clinically indicated for cutaneous skin lesions
Bone	If clinically indicated	If clinically indicated	If clinically indicated	If clinically indicated

The process for image collection and transmission to the central vendor can be found in the Site Imaging Manual. Information for disease assessments may be submitted for central review.

Immunotherapeutic agents, such as MK-1966 and SD-101 may produce antitumor effects by potentiating endogenous cancer-specific immune response. The response patterns seen with such an approach may extend beyond the typical time course of responses seen with typical cytotoxic agents, and can manifest a clinical response after an initial increase in tumor burden or even the appearance of new lesions. Therefore, the subject should not be discontinued from the trial until PD is confirmed.

7.1.2.6.3.2 Tumor Tissue Collection and Correlative Studies Blood Sampling

Subjects may provide tumor sample(s) as specified in Procedures Manual. Sample collection, storage and shipment instructions for correlative study samples, archival tumor samples and newly obtained biopsy specimens will be provided in the Procedures Manual. Archival samples are not required to be submitted within the screening period.

7.1.3 Laboratory Procedures/Assessments

Details regarding specific laboratory procedures/assessments to be performed in this trial are provided below. The total amount of blood/tissue to be drawn/collected over the course of the trial (from pre-trial to post-trial visits), including approximate blood/tissue volumes drawn/collected by visit and by sample type per subject can be found in the Procedure Manual.

7.1.3.1 Laboratory Safety Evaluations (Hematology, Chemistry and Urinalysis)

Laboratory tests for hematology, chemistry and urinalysis are specified in [Table 10](#).

Table 10 Laboratory Tests

Hematology	Chemistry	Urinalysis	Other
Hematocrit	Albumin	Blood	Serum β -human chorionic gonadotropin (β -hCG) ^a
Hemoglobin	Alkaline phosphatase	Glucose	Hepatitis HBsAg
Platelet count	Alanine aminotransferase (ALT)	Protein	Hepatitis C (HCV RNA) or Hepatitis C antibody
WBC (total and differential)	Aspartate aminotransferase (AST)	Specific gravity	HIV
RBC	Bicarbonate or carbon dioxide (CO_2) ^b	Microscopic exam, if abnormal results are noted	blood for correlative studies
Absolute neutrophil count	Calcium	Urine pregnancy test ^a	Blood for genetics
	Chloride		PT (INR) ^d
	Creatinine		aPTT/PTT ^d
	Glucose		TSH (TSH, Free T ₄ , Total T ₃)
	Lactate dehydrogenase (LDH)		
	Phosphorus		
	Potassium		
	Sodium		
	Total Bilirubin		
	Direct Bilirubin, if total bilirubin is elevated above the upper limit of normal		
	Total protein		
	Blood Urea Nitrogen		
	Urea ^c		
	Uric acid		

a. Perform on women of childbearing potential only. Urine pregnancy test is preferred. If the urine test is positive or cannot be confirmed as negative, a serum pregnancy test will be required.
 b. If these tests are not done as part of standard of care in your region then these tests do not need to be performed.
 c. Blood Urea Nitrogen is preferred; if not available urea may be tested.
 d. Coagulation factors (PT/INR and aPTT/PTT) should be tested as part of the screening procedures for all subjects. Any subject receiving anticoagulant therapy should have coagulation factors monitored closely throughout the trial.

Laboratory tests for Screening should be performed within 7 days prior to the first dose of MK-1966 and SD-101. After Cycle 1, pre-dose laboratory tests can be performed up to 72 hours prior to dosing. Results must be reviewed by the investigator of qualified designee and found to be acceptable prior to each dose of study treatment

7.1.3.2 Pharmacokinetic/Pharmacodynamic Evaluations

7.1.3.2.1 Blood Collection (Serum) for MK-1966

Sample collection, storage and shipment instructions for PK samples will be provided in the Procedure Manual.

The time points for PK sampling are described in Section 6.0-Trial Flow Chart.

7.1.3.2.2 Blood Collection for Anti- MK-1966 Antibodies (ADA)

Sample collection, storage and shipment instructions for anti-MK-1966 antibodies (ADA) samples will be provided in the Procedures Manual.

The timepoints for PK sampling are described in Section 6.0-Trial Flow Chart.

7.1.3.3 Planned Genetic Analysis Sample Collection

Sample collection, storage and shipment instructions for Planned Genetic Analysis samples will be provided in the Procedures Manual. Sample(s) should be drawn for planned analysis of the association between genetic variants in DNA and drug response. If there is either a documented law or regulation prohibiting collection, or if the IRB/IEC does not approve the collection of the sample for these purposes, then this sample will not be collected at that site. If the sample is collected, leftover extracted DNA will be stored for future biomedical research if the subject signs the FBR consent. If the planned genetic analysis is not approved, but FBR is approved and consent is given, this sample will be collected for the purpose of FBR.

7.1.3.4 Future Biomedical Research Sample Collection

The following specimens are to be obtained as part of Future Biomedical Research:

- Leftover DNA for future research.
- Leftover main study tumor stored for future research
- Leftover RNA
- Leftover Serum and Plasma

7.1.4 Other Procedures

7.1.4.1 Withdrawal/Discontinuation

Subjects who discontinue/withdraw from treatment prior to completion of the treatment/ regimen should be encouraged to continue to be followed for all remaining study visits.

When a subject discontinues/withdraws from participation in the trial, all applicable activities scheduled for the final trial visit should be performed at the time of discontinuation. Any adverse events which are present at the time of discontinuation/withdrawal should be followed in accordance with the safety requirements outlined in Section 7.2 - Assessing and Recording Adverse Events. .

7.1.4.1.1 Withdrawal From Future Biomedical Research

Subjects may withdraw their consent for Future Biomedical Research and have their specimens and all derivatives destroyed. Subjects may withdraw consent at any time by contacting the principal investigator for the main trial. If medical records for the main trial are still available, the investigator will contact the Sponsor using the designated mailbox ([contact]), and a form will be provided by the Sponsor to obtain appropriate information to complete specimen withdrawal. Subsequently, the subject's specimens will be removed from the biorepository and be destroyed. A letter will be sent from the Sponsor to the investigator confirming the destruction. It is the responsibility of the investigator to inform the subject of completion of destruction. Any analyses in progress at the time of request for destruction or already performed prior to the request being received by the Sponsor will continue to be used as part of the overall research trial data and results. No new analyses would be generated after the request is received.

In the event that the medical records for the main trial are no longer available (e.g., if the investigator is no longer required by regulatory authorities to retain the main trial records) or the specimens have been completely anonymized, there will no longer be a link between the subject's personal information and their specimens. In this situation, the request for specimen destruction cannot be processed.

7.1.4.2 Blinding/Unblinding

This is an open label trial; there is no blinding for this trial.

7.1.4.3 Calibration of Critical Equipment

The investigator or qualified designee has the responsibility to ensure that any critical device or instrument used for a clinical evaluation/test during a clinical trial that provides important information about inclusion/exclusion criteria and/or safety or efficacy parameters shall be suitably calibrated and maintained to ensure that the data obtained is reliable and/or reproducible. Documentation of equipment calibration must be retained as source documentation at the trial site.

Critical Equipment for this trial includes:

- Laboratory equipment – as required for inclusion labs and trial assessments
- Imaging equipment – as required for study objectives
- ECG equipment- as required for trial assessments
- Infusion syringe and/or pump – used to administer MK-1966 and SD-101

7.1.5 Visit Requirements

Visit requirements are outlined in Section 6.0 - Trial Flow Chart. Specific procedure-related details are provided above in Section 7.1 - Trial Procedures.

7.1.5.1 Screening

Approximately 28 days prior to randomization, potential subjects will be evaluated to determine that they fulfill the entry requirements as set forth in Section 5.1.

Screening procedures may be repeated after consultation with the Sponsor.

Written consent must be obtained prior to performing any protocol specific procedure. Results of a test performed prior to the subject signing consent as part of routine clinical management are acceptable in lieu of a screening test if performed within the specified time frame. Screening procedures are to be completed within 28 days prior to the first dose of trial treatment except for the following:

- Screening laboratory tests are to be performed within 7 days prior to the first dose of trial treatment.
- For women of reproductive potential, a urine pregnancy test will be performed within 72 hours prior to first dose of trial treatment. If urine pregnancy results cannot be confirmed as negative, a serum pregnancy test, performed by the local study site laboratory, will be required.
- Tumor imaging must be performed within 28 days prior to the first dose of trial treatment.

7.1.5.2 Treatment Period

Visit requirements are outlined in Section 6.0 - Trial Flow Chart. Specific procedure-related details are provided above in Section 7.1 - Trial Procedures.

After a screening phase of up to 28 days, eligible subject(s) will be assigned a dose levels by the sponsor. MK-1966 and SD- 101 treatment will be administered as outlined in Section 5.2 for 8 cycles (approximately 24 weeks) of study medication in Part A, B, C, or administrative reasons requiring cessation of treatment. After the end of treatment (EOT), each subject will be followed for 30 days. Serious adverse events (SAEs) will be collected for 30 days after EOT.

7.1.5.2.1 Safety Follow-up Visit

The mandatory Safety Follow-Up Visit should be conducted approximately 30 days after the last dose of trial treatment or before the initiation of a new antineoplastic treatment, whichever comes first. Subjects with an AE of Grade >1 will be further followed until the resolution of the AE to Grade 0-1 or until beginning of a new antineoplastic therapy, whichever occurs first.

Visit requirements are outlined in Section 6.0 - Trial Flow Chart.

7.2 Assessing and Recording Adverse Events

An adverse event is defined as any untoward medical occurrence in a patient or clinical investigation subject administered a pharmaceutical product and which does not necessarily have to have a causal relationship with this treatment. An adverse event can therefore be any unfavourable and unintended sign (including an abnormal laboratory finding, for example), symptom, or disease temporally associated with the use of a medicinal product or protocol-specified procedure, whether or not considered related to the medicinal product or protocol-specified procedure. Any worsening (i.e., any clinically significant adverse change in

frequency and/or intensity) of a preexisting condition that is temporally associated with the use of the Sponsor's product, is also an adverse event.

Changes resulting from normal growth and development that do not vary significantly in frequency or severity from expected levels are not to be considered adverse events. Examples of this may include, but are not limited to, teething, typical crying in infants and children and onset of menses or menopause occurring at a physiologically appropriate time.

Sponsor's product includes any pharmaceutical product, biological product, device, diagnostic agent or protocol-specified procedure, whether investigational (including placebo or active comparator medication) or marketed, manufactured by, licensed by, provided by or distributed by the Sponsor for human use.

Adverse events may occur during clinical trials, or as prescribed in clinical practice, from overdose (whether accidental or intentional), from abuse and from withdrawal.

All adverse events that occur after the consent form is signed but before treatment allocation/randomization must be reported by the investigator if they cause the subject to be excluded from the trial, or are the result of a protocol-specified intervention, including but not limited to washout or discontinuation of usual therapy, diet, placebo treatment or a procedure. From the time of treatment allocation/randomization through 14 days following cessation of treatment, all adverse events must be reported by the investigator. Such events will be recorded at each examination on the Adverse Event case report forms/worksheets. The reporting timeframe for adverse events meeting any serious criteria is described in section 7.2.3.1. The investigator will make every attempt to follow all subjects with non-serious adverse events for outcome.

Electronic reporting procedures can be found in the Electronic Data Capture (EDC) data entry guidelines. Paper reporting procedures can be found in the Investigator Trial File Binder (or equivalent).

Adverse events will not be collected for subjects during the pre-screening period (for determination of archival tissue status) as long as that subject has not undergone any protocol-specified procedure or intervention. If the subject requires a blood draw, fresh tumor biopsy etc., the subject is first required to provide consent to the main study and AEs will be captured according to guidelines for standard AE reporting.

7.2.1 Definition of an Overdose for This Protocol and Reporting of Overdose to the Sponsor

For purposes of this trial, an overdose will be defined as any dose exceeding (by > 50%) the prescribed dose for SD-101 and/or MK-1966. No specific information is available on the treatment of overdose of MK-1966. In the event of overdose, MK-1966 should be discontinued and the subject should be observed closely for signs of toxicity. Appropriate supportive treatment should be provided if clinically indicated.

If an adverse event(s) is associated with ("results from") the overdose of Sponsor's product or vaccine, the adverse event(s) is reported as a serious adverse event, even if no other seriousness criteria are met.

If a dose of Sponsor's product or vaccine meeting the protocol definition of overdose is taken without any associated clinical symptoms or abnormal laboratory results, the overdose is MK-1966-001-03 Final Protocol

9-Feb-2017

Confidential

reported as a non-serious Event of Clinical Interest (ECI), using the terminology “accidental or intentional overdose without adverse effect.”

All reports of overdose with and without an adverse event must be reported by the investigator within 24 hours to the Sponsor either by electronic media or paper. Electronic reporting procedures can be found in the EDC data entry guidelines. Paper reporting procedures can be found in the Investigator Trial File Binder (or equivalent).

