- g. MK-1966 Pharmacokinetics (PK) samples will be collected more frequently in Cycles 1-3. On Days 1, 22 and 43 -collect predose, at the end of infusion and 2h after the start of the infusion (+10 minutes). On Day1 of Cycles 4-8 collect PK samples predose. Also collect PK Samples on Days 2, 3, 8, 15, 29, 36, 50, 57, at the treatment discontinuation, and Safety Follow-up visit (30 days post end of treatment).
- h. Blood samples for IL-10 Pharmacodynamics (PD) will be drawn at Screening and at times that match PK sampling in footnote “i” above.
- i. Unilateral bone marrow biopsy and aspirate will be performed at Screening if not previously performed or if performed more than 90 days previously with negative results. The bone marrow biopsy will be performed to confirm a CR if the subject was initially positive or if it is clinically indicated by new abnormalities in the peripheral blood counts or blood smear (section 4.2.3.5)
- j. When SD-101 and MK-1966 are scheduled on the same day, SD-101 will be administered first. MK-1966 will be administered at least 30 minutes after the SD-101 injection.
- k. These samples may be performed up to 72 hours prior to dosing. However, in Cycle 1 on Day 1, samples are to be drawn prior to dosing and should be used as the subject's baseline (not screening) values.
- l. Include HCV, RNA (qualitative) or Hepatitis C antibody, HBsAg, and HIV type 1 and type 2 (e.g., HIV-1/-2 antibody screening test and evaluation of HIV viral load as needed).
- m. Patients who discontinue from treatment or have completed post treatment follow up should be contacted every three months to monitor overall survival (for up to 2 years from last dose of study drug or until the sites are notified by the Sponsor that the survival follow up is no longer required).
- n. The Day 9 visit must be 24 hours (+/- 4 hours) after the Day 8 visit.
- o. Sample(s) and/or procedures will be collected prior to dosing and when applicable as outlined in the Procedures Manual.
- p. Record all AEs occurring from signing of informed consent until 30 days after the last dose of MK-1966 and SD-101. Report all SAEs occurring up to 30 days after the last dose of treatment
- q. Dosing with MK-1966 and/or SD-101 will occur within the timeframes outlined in section 5.2.5. and/or the Procedures Manual.
- r. After the SD-101 is injected, the injection site should be observed every 15 minutes for at least 90 minutes.

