7.2.2 Reporting of Pregnancy and Lactation to the Sponsor

Although pregnancy and lactation are not considered adverse events, it is the responsibility of investigators or their designees to report any pregnancy or lactation in a subject (spontaneously reported to them) that occurs during the trial.

Pregnancies and lactations that occur after the consent form is signed but before treatment allocation/randomization must be reported by the investigator if they cause the subject to be excluded from the trial, or are the result of a protocol-specified intervention, including but not limited to washout or discontinuation of usual therapy, diet, placebo treatment or a procedure. Pregnancies and lactations that occur from the time of treatment allocation/randomization through 14 days following cessation of Sponsor's product must be reported by the investigator. All reported pregnancies must be followed to the completion/termination of the pregnancy. Pregnancy outcomes of spontaneous abortion, missed abortion, benign hydatidiform mole, blighted ovum, fetal death, intrauterine death, miscarriage and stillbirth must be reported as serious events (Important Medical Events). If the pregnancy continues to term, the outcome (health of infant) must also be reported.

Such events must be reported within 24 hours to the Sponsor either by electronic media or paper. Electronic reporting procedures can be found in the EDC data entry guidelines. Paper reporting procedures can be found in the Investigator Trial File Binder (or equivalent).

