7.2.3 Immediate Reporting of Adverse Events to the Sponsor

7.2.3.1 Serious Adverse Events

A serious adverse event is any adverse event occurring at any dose or during any use of Sponsor's product that:

- Results in death;
- Is life threatening;
- Results in persistent or significant disability/incapacity;
- Results in or prolongs an existing inpatient hospitalization;
- Is a congenital anomaly/birth defect;
- Is an other important medical event.

Note: In addition to the above criteria, adverse events meeting either of the below criteria, although not serious per ICH definition, are reportable to the Sponsor in the same timeframe as SAEs to meet certain local requirements. Therefore, these events are considered serious by the Sponsor for collection purposes.

- Is a new cancer (that is not a condition of the study);
- Is associated with an overdose.

Refer to [Table 11](#) for additional details regarding each of the above criteria.

Progression of the cancer under study is not considered an adverse event unless it results in hospitalization or death.

For the time period beginning when the consent form is signed until treatment allocation/randomization, any serious adverse event, or follow up to a serious adverse event, including death due to any cause, that occurs to any subject must be reported within 24 hours to the Sponsor if it causes the subject to be excluded from the trial, or is the result of a protocol-specified intervention, including but not limited to washout or discontinuation of usual therapy, diet, placebo treatment or a procedure.

For the time period beginning at treatment allocation/randomization through 14 days following cessation of treatment, any serious adverse event, or follow up to a serious adverse event, including death due to any cause, whether or not related to the Sponsor's product, must be reported within 24 hours to the Sponsor either by electronic media or paper. Electronic reporting procedures can be found in the EDC data entry guidelines. Paper reporting procedures can be found in the Investigator Trial File Binder (or equivalent).

Additionally, any serious adverse event, considered by an investigator who is a qualified physician to be related to the Sponsor's product that is brought to the attention of the investigator at any time outside of the time period specified in the previous paragraph also must be reported immediately to the Sponsor.

All subjects with serious adverse events must be followed up for outcome.

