
7.2.3.2 Events of Clinical Interest

Selected non-serious and serious adverse events are also known as Events of Clinical Interest (ECI) and must be reported to the Sponsor.

For the time period beginning when the consent form is signed until treatment allocation/randomization, any ECI, or follow up to an ECI, that occurs to any subject must be reported within 24 hours to the Sponsor if it causes the subject to be excluded from the trial, or is the result of a protocol-specified intervention, including but not limited to washout or discontinuation of usual therapy, diet, placebo treatment or a procedure.

For the time period beginning at treatment allocation/randomization through 14 days following cessation of treatment, any ECI, or follow up to an ECI, whether or not related to the Sponsor's product, must be reported within 24 hours to the Sponsor, either by electronic media or paper. Electronic reporting procedures can be found in the EDC data entry guidelines. Paper reporting procedures can be found in the Investigator Trial File Binder (or equivalent).

Events of clinical interest for this trial include:

1. an overdose of Sponsor's product, as defined in Section 7.2.1 - Definition of an Overdose for This Protocol and Reporting of Overdose to the Sponsor, that is not associated with clinical symptoms or abnormal laboratory results.
2. an elevated AST or ALT lab value that is greater than or equal to 3X the upper limit of normal and an elevated total bilirubin lab value that is greater than or equal to 2X the upper limit of normal and, at the same time, an alkaline phosphatase lab value that is less

than 2X the upper limit of normal, as determined by way of protocol-specified laboratory testing or unscheduled laboratory testing.*

*Note: These criteria are based upon available regulatory guidance documents. The purpose of the criteria is to specify a threshold of abnormal hepatic tests that may require an additional evaluation for an underlying etiology. The trial site guidance for assessment and follow up of these criteria can be found in the Investigator Trial File Binder (or equivalent).

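### AE and any-causality SAE reporting ends 14 days after an undefined point in Sections 7.2 and 7.2.3.1 but at 30 days elsewhere, on two anchors; the Section 8.2 lock can precede the last safety visits

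*Combined protocol and SAP*

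**What the plan says.** **14-day passages.** Section 7.2 states: "From the time of treatment allocation/randomization through 14 days following cessation of treatment, all adverse events must be reported by the investigator". It then sends SAE timing elsewhere: "The reporting timeframe for adverse events meeting any serious criteria is described in section 7.2.3.1". Section 7.2.3.1 reads: "For the time period beginning at treatment allocation/randomization through 14 days following cessation of treatment, any serious adverse event", and requires reporting within 24 hours. It makes one exception: an SAE that the investigator judges related and learns of "at any time outside of the time period specified in the previous paragraph also must be reported immediately to the Sponsor". Section 7.2.3.2 uses the 14-day limit for events of clinical interest (ECIs). *Cessation of treatment* is not defined in any of these sections.

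**30-day passages.** Flow-chart footnote p (Section 6.0) states: "Record all AEs occurring from signing of informed consent until 30 days after the last dose of MK-1966 and SD-101". It also has all SAEs reported up to 30 days after the last dose. Sections 1.0 and 7.1.5.2 collect SAEs for 30 days after EOT.

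**Anchors.** Section 7.1.5.2.1 times the mandatory Safety Follow-up Visit at about 30 days after the last dose, or before a new antineoplastic treatment if that comes first. The flow-chart column times it from the end of the Treatment Period, and footnote g from the end of treatment. The End of Treatment Period column is set at the end of Cycle 8 or the time of discontinuation, and footnote s places the end of Cycle 8 at Day 168.

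**Lock.** Section 8.2 locks the database approximately 24 weeks after the last subject is enrolled. No later lock or safety update is described.

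**The concern.** Two sites can each follow the protocol and collect different data. One works from Sections 7.2 and 7.2.3.1 and stops at 14 days; the other works from Section 6.0 and continues to 30. Non-serious AEs and SAEs judged unrelated would then be observed for different lengths of time by site and pooled as if the time were equal.

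Safety and tolerability is the primary objective. Section 8.6.2 plans percentages of subjects in five AE categories at the recommended phase 2 dose (RPTD), with 80% Clopper-Pearson intervals. A lock that falls before the last safety visits would cut short the same summaries for the latest enrollees.

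**Working it through.** **Inputs.** Table 5: MK-1966 on Day 1, then every 3 weeks for 7 more doses; SD-101 on Days 1, 8, 15 and 22, then every 3 weeks for 6 more. Footnote s: end of Cycle 8 at Day 168. Section 8.2: lock at about 24 weeks. Section 8.6.3.5: one subject enrolled per week.

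**Reproducing Day 168.** Last MK-1966 dose: 1 + 7 × 21 = Day 148. Last SD-101 dose: 22 + 6 × 21 = Day 148. Eight cycles last 8 × 21 = 168 days, which matches footnote s. Counting 21 days on from Day 148 gives Day 169, so the footnote's two expressions differ by one day. I use 168.

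**Window ends for a subject with eight undelayed cycles**

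| Rule | Arithmetic | Ends |
|---|---|---|
| 14 days, cessation = last dose | 148 + 14 | Day 162 |
| 14 days, cessation = end of Treatment Period | 168 + 14 | Day 182 |
| Footnote p, last dose + 30 | 148 + 30 | Day 178 |
| Sections 1.0 and 7.1.5.2, EOT + 30 | 168 + 30 | Day 198 |

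- SAE gap against Sections 1.0 and 7.1.5.2: 198 − 162 = 36 days, or 198 − 182 = 16 days.
- AE and SAE gap against footnote p: 178 − 162 = 16 days if cessation means the last dose. If it means the end of the Treatment Period there is no gap; the 14-day rule runs 182 − 178 = 4 days longer. The undefined term thus decides even the direction of this conflict.

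**Lock.** 24 × 7 = 168 days after enrollment, with enrollment taken as Day 1 (the case most favorable to the plan). Day 178 is 177 days after Day 1, so the visit follows the lock by 177 − 168 = 9 days. Day 198 is 197 days after, so 197 − 168 = 29 days.

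A subject enrolled k weeks before the last one is 168 + 7k days past Day 1 at lock. The visit is still to come when this is below 177 (k = 0, 1: 2 subjects) or below 197 (k = 0 to 4: 5 subjects), if all receive Cycle 8. That is 2/64 = 3.1% to 2/52 = 3.8%, or 5/64 = 7.8% to 5/52 = 9.6%, of the plan's two scenario totals. The Section 5.2.5 dosing window (−3/+5 days) and an assumed ±3-day visit window shift the visit by −6 to +8 days, giving 1 to 3 or 4 to 6 subjects.

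**Effect on the serious-AE percentage.** Each RPTD subject whose only SAE is unrelated and falls in the gap moves it by 1/N. The plan does not fix N for this summary, so I show a range, with assumed true rates of about 20% and 40%.

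| Assumed N at RPTD | Shift per subject | Width of 80% Clopper-Pearson interval |
|---|---|---|
| 20 (as in Table 12) | 5.0 points | 27.0 (4/20) to 31.8 (8/20) |
| 40 (Parts B and C) | 2.5 points | 18.4 (8/40) to 21.9 (16/40) |
| 46 (plus 6 from Part A) | 2.2 points | 17.0 (9/46) to 20.3 (18/46) |

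In each row one such subject is small against the interval.

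**The case against.** **The flow chart governs.** Section 2.1 refers to the flow chart for procedure times and visit windows, Section 7.1.2.1 refers to it for AE assessment, and the chart marks AE review at the mandatory 30-day visit under footnote p. This stands in part: a site that makes the visit is pointed to 30 days. It does not settle the matter, because Section 7.2 expressly sends SAE timing to Section 7.2.3.1, where the limit is 14 days.

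**Recording differs from reporting.** Recording to Day 30 would satisfy every passage, and none tells a site to stop at 14 days. But the verbs do not divide that way. Section 7.2 has the events in its 14-day window recorded on the AE forms, and footnote p has SAEs reported to 30 days.

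**Scope.** A reader might infer that the ECI and pregnancy windows are contradicted as well. No 30-day passage names ECIs; footnote p reaches them only because they are selected adverse events. No 30-day passage covers pregnancy, and Section 7.2.2 has its own anchor: "14 days following cessation of Sponsor's product must be reported by the investigator". That window is not contradicted. A reader might also call EOT undefined, but the flow chart gives it a working definition. Treating EOT as Day 148 while cessation means Day 168, which would remove the SAE gap, is therefore implausible.

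**Lock.** On the last-dose anchor of Section 7.1.5.2.1, 9 days may fit within approximately 24 weeks. That is fair; 29 days would not reasonably fit. The visit also moves earlier if a new antineoplastic treatment starts, and the subject counts assume that every late enrollee receives Cycle 8.

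**Conclusion.** The conflict over AE and any-causality SAE windows is in current text and is not resolved by it. For a Cycle 8 completer, the SAE gap against Sections 1.0 and 7.1.5.2 is 16 or 36 days; against footnote p the AE and SAE gap is 16 days or none. The lock precedes the last safety visit by about 9 days (arguably acceptable) or about 29 days, affecting about 2 or 5 subjects. These figures assume undelayed cycles, enrollment on Day 1, one subject per week, and Cycle 8 received by all late enrollees.

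The consequence is limited to the descriptive Section 8.6.2 summaries, mainly the serious-AE percentage. The category that is both drug-related and serious is protected, because related SAEs stay reportable at any time. Discontinuation due to an AE can hardly change after treatment ends. The any-AE and drug-related-AE percentages change only for a subject with no such event earlier.

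A reader might infer a threat to the primary endpoint or to dose decisions. The documents do not support that: DLTs are assessed over 21 days, and Table 6 uses only DLTs. Nor would deaths go unseen, since survival follow-up (footnote m) captures them, though possibly not as SAEs. AEs above Grade 1 at the safety visit are followed until they resolve to Grade 0-1 or a new therapy starts. This is a minor consistency correction.

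**What to change.** 1. Define *cessation of treatment*. Reconcile Sections 1.0, 6.0 (safety-visit column, footnotes g and p), 7.1.5.2, 7.1.5.2.1, 7.2 and 7.2.3.1 to one AE/SAE window and one anchor that covers the already mandatory 30-day Safety Follow-up Visit. Include Section 7.2.3.2 for consistency. Section 7.2.2 need not be part of this.
2. State any window that the choice shortens. Thirty days from the last dose ends on Day 178 and takes 198 − 178 = 20 days off the SAE collection in Sections 1.0 and 7.1.5.2, with EOT at Day 168. Thirty days from the end of the Treatment Period ends on Day 198 and shortens none of the stated AE, SAE or ECI windows.
3. In Section 8.2, lock only after the last subject's Safety Follow-up Visit.

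The cost is amendment wording and a lock about 9 or 29 days later, depending on the anchor. No new visit is needed.
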